##### **4.4.3 Transcranial Magnetic Stimulation (TMS) Procedure**

Before and after TMS, patients will be screened for hearing by the NIH Audiology Service. Each test will take up to 30 minutes. TMS will be applied using a coil placed on the scalp. Surface EMG will be recorded from the first dorsal interosseus (FDI) muscle. The coil will be manually positioned, and the electrode position will be marked with a pen for eliciting motor evoked potentials (MEPs)

from the FDI muscle. After the subject is seated in a comfortable position, an adjustable head restraint will be applied to prevent head movements. Indices for cortical excitability will be obtained including motor threshold (MT), recruitment curve, intracortical inhibition (ICI), intracortical facilitation (ICF), and cortical silent period (CSP) from motor cortex.

The MT is defined as the minimum percentage of the stimulator output that evoked a motor evoked potential of more than 50  $\mu$ V in at least 5 out of 10 trials. For recruitment curve determination, TMS will be applied over the same hemisphere from which MT is measured, while 5 responses are recorded at each of a range of different stimulus intensities. Stimulus intensity will be increased in steps of 10% of the individual MT from 90 to 160% MT. MEP size will be measured peak-to-peak in single trials and averages will be calculated for each intensity. ICI and ICF will be studied using a paired stimulus paradigm. The conditioning stimulus (70% MT) followed by the test stimulus (120% MT) will be delivered at 3 different interstimulus intervals (ISI); 2 ms for short ICI, 10 ms for ICF, and 100 ms for long ICI. Each run will consist of 10 trials, and the amplitude ratio of the mean conditioned MEP to control MEP will be determined for each ISI. Measurement of the CSP will be carried out from the tonically active FDI, performing 10 trials each of the intensities at 10, 20, 30, and 40% above MT. CSP onset and termination will be measured in the rectified single trials as the times of the end of the preceding MEP and the return of sustained activity in the EMG, respectively. The conditional averages will be calculated from the single-trial data. TMS will take up to 90 minutes.

#### 4.4.4 Neuropsychological Assessments

Patients will undergo comprehensive language and cognitive evaluations using a selection of assessments based on age and ability such as the following:

1. WNV (Wechsler Nonverbal Scale of Ability) for patients up to age 22, an individually-administered, standardized test that provides an IQ score and insights into cognitive functioning. The test requires approximately 30 minutes to administer.
2. WAIS-IV (Wechsler Adult Intelligence Scale) for patients age 22 and older, also an individually-administered test of ability will be administered using the subtests that overlap the WNV. These are nonverbal because of the language limitations of this population.
3. The Neuropsychological Assessment Battery: Language Module. Subtests to be administered include confrontation Naming and following directions (Auditory Comprehension) to assess language competence.

4. Rule Shift from the Behavioral Assessment of Dysexecutive Syndrome is a short (5 minute) test of working memory.

5. Computerized tests of reaction time and go-no-go to assess the constructs of reaction time and attention.

6. Texas Functional Living Scale is an assessment of practical reading, math, language comprehension and memory developed for individuals with cognitive limitations.

7. ABAS: Adaptive Behavior Assessment Scale to be completed by parent. Queries on functional skills.

8. Wechsler Preschool and Primary Scale of Intelligence-IV (WPPSI-IV), for patients between the ages of 2.5 and 7, is an individually-administered, standardized test that provides scores for verbal and nonverbal domains of intellectual ability. The test requires between 45 minutes and 75 minutes to administer, depending on the age.

9. Wechsler Intelligence Scale for Children-V (WISC-V), for patients 6 years of age through age 17, is an individually administered, standardized test of cognitive ability. This test provides scores for verbal and nonverbal domains of intellectual ability. The test requires between 60 minutes and 90 minutes to administer, depending on age

#### 4.4.5 Lumbar Puncture Procedure (OPTIONAL):

Lumbar puncture will be performed according to standard procedure utilizing sterile technique in the lateral recumbent position. Lumbar puncture will be carried out in the awake state utilizing local 1% lidocaine anesthesia. Approximately ten ml of CSF will be collected for routine studies and special metabolites including GABA-related compounds and biogenic amines. The fluid designated for special metabolites will be placed immediately in dry ice and then stored in a -70 degree freezer.

#### 4.4.6 EEG

EEG will be performed according to standard procedures using the international 10-20 standard method of electrode placement.

#### 4.4.7 Blood draw

Approximately ten cubic centimeters of blood will be drawn at screening, and at the end of each treatment phase, for CBC, clinical chemistry, and hepatic panels.

#### 4.4.8 Seizure and side effect calendar

Patients and families will be asked to keep a record of seizures and any possible medication side effects.

#### 4.4.9: Pregnancy tests

Patients of child-bearing potential will have a urine pregnancy test at screening and each out-patient visit. Pregnancy testing may also be done based on safety monitoring and clinical assessment. Pregnancy testing may be done by local providers. In this case, we will have patients designate the local provider in advance. We will contact the local provider and arrange for payment of testing by the NIH and also document a plan in the progress notes for how individual providers will communicate test results. We will request local providers provide written documentation of pregnancy testing results by facsimile to include in the NIH patient medical record.

As outlined in the minor assents, if the pregnancy testing for a minor patient, performed at the NIH or through a local provider, is positive, we will inform the parent or guardian.

### **4.5 Drug Treatment**

#### 4.5.1 Randomization

A crossover design will be employed where patients are randomized into a six-month trial of treatment versus placebo.

Subjects will be randomized at the end of baseline testing to either active drug or placebo using a 1:1 ratio per the randomization schedule. The randomization schedule will be generated, secured, distributed, and stored by the NIH Pharmacy.

#### 4.5.2 Study Drug Administration

Patients may be outpatients or inpatients during titration. The first dose of study pills will be administered at the NIH. The patient will stay for 30 – 90 minutes following the first dose. The patient will be permitted to return to local accommodations overnight and return 12 - 24 hours after the first dose to be assessed for any skin reactions, and then discharged home.

All patients will be given an exact written titration schedule to follow, and will be contacted by phone and/or clinical trials database at least every two weeks during the study.

Following a 9 week +/- 2 weeks total washout period, including drug taper, described below, patients will enter the other treatment arm. For the second phase of the study patients may also be inpatients or outpatients. The first dose of study pills will be administered at the NIH. The patient will stay for 30 – 90 minutes following the first dose. The patient will be permitted to return to local accommodations overnight and return 12 – 24 hours after the first dose to be assessed for any skin reactions, and then discharged home.

The active treatment will be SGS-742, synthesized by IRIX pharmaceuticals in a GCP facility. The target dose will be 10 mg/kg with a maximum of 600 mg given orally three times daily for six months, with an increasing titration over nine to fifteen days. The placebo arm will be inert placebo given orally three times daily. It is recommended to take the medication three times each day prior to meals because administration of food decreases oral systemic availability of SGS-742. The drug and matching placebo will be encapsulated by the NIH pharmacy. The pharmacy will draw up a randomization schedule and ensure blinding.

Patients and examining physicians will be blinded as to the treatment arm in which the patient is enrolled.

The NIH Pharmacy will dispense three month's supply of study drug (SGS-742 or placebo) to subjects for each study treatment phase. The second three-month supply can be picked up by the patient or sent by mail. Patients will be asked to bring study pill bottles to each clinic visit. Pill counts will be performed at each visit if patients bring study pill bottles. Patients will be advised to take a missed dose if they remember within 4 hours; otherwise, to take the next scheduled dose and record the missed dose on their seizure/medication calendar. Patients will be advised to take their study drug about one hour before food.

All unused investigational product will be returned to the NIH Pharmacy for disposal if patients bring study pill bottles.

At the end of phase 2, the study drug will be tapered off as described below. If patients only get one or two doses the first day, an additional day may be added to the titration and taper schedule. Patients will have a final follow-up visit four to seven weeks after completion of the final drug taper.

#### 4.5.3 Drug titration

The following drug /placebo titration schedule will be used for patients weighing 30 kg or greater:

2.5 mg/kg/dose (up to 150 mg) tid X 3 days;  
5 mg/kg/dose (up to 300 mg) tid X 3 days;  
7.5 mg/kg/dose (up to 450 mg) tid X 3 days;  
10 mg/kg/dose (up to 600 mg) tid (target dose).

The drug is only available in 75- and 150-mg capsules. Thus, for patients weighing less than 30 kg, the dosing regimen may be modified to reflect the use of specific size capsules and dose limits for small participants.

Dosing may be modified as close as possible to the weight-specified dose without exceeding it. Modified dosing schedules for children weighing less than 30 kg will allow us to come as close as possible to the final weight-based protocol-specified dose without exceeding it. The dosing schedule in these

children may be modified from TID dosing to QD and BID to extend the titration period to avoid large dose jumps between titration levels.

If patients experience side effects, the next scheduled dose increase will be delayed until they abate. If this does not occur, the dose will be reduced in 2.5 mg/kg per day increments until side effects abate.

The final maximum dose will be determined by the patient's weight but will not exceed 600 milligrams three times per day.

#### 4.5.4 Drug taper schedule

The following drug /placebo taper will follow the reverse schedule of the drug titration:

For patients weighing 30 kg or greater:

7.5 mg/kg/dose (up to 450 mg) tid X 3 days;

5 mg/kg/dose (up to 300 mg) tid X 3 days;

2.5 mg/kg/dose (up to 150 mg) tid X 3 days;

then stop.

For patients weighing less than 30 kg:

The drug /placebo taper will follow the reverse schedule of the drug titration for each patient.

Placebo will be titrated and tapered in capsules matching the SGS-742 dosing stages.

## 4.6 Sedation

For adults needing sedation for optional MRI/MRS, the NIH Anesthesia Department will use Dexmedetomidine, a highly selective alpha-adrenoreceptor agonist that exerts its hypnotic effects at the locus coeruleus, and has minimal cardiovascular and virtually no respiratory depressant effects (Correa-Sales 1992; Maze et al 2001; Nelson LE 2003). In addition, the drug has no effect on release or extracellular levels of glutamate, aspartate and GABA (Valtonen et al 1995). It has been shown to be a safe and well-tolerated agent, and is approved by the FDA for use in the intensive care unit setting. The drug is routinely used clinically in intensive care units and operating rooms, and for imaging studies (Mason 2008, Yuen 2008). According to the package insert, adverse effects in clinical trials included hypotension (28% versus 13% in patients receiving placebo), hypertension (16% versus 18%), nausea (11% versus 9%) and bradycardia (7% versus 3%). This medication was used without incident in our previous SSADH deficiency study. If sedation is required for MRI/MRS, the LP

may be done while under sedation. No sedation will be used for research purposes in minors.

#### **4.7 End of Participation**

Participants will remain under the care of their own physicians while in this study. The study physicians may, in cooperation with the treating physicians, manage neurologic treatment.

Clinically relevant results of study procedures such as MRI findings will be given to the patients and their parents or guardians.

Study phase	Length	Clinic visit, physical exam	SGS-742 or placebo	EEG	Blood tests	Urine tests	EKG	Lumbar puncture *	MRI MR S*	TMS	NP tests
Screening	1-3 days	X			X	X	X				
Baseline	1-3 days	X		X				X	X	X	X
Titration	9 -15 days		X								
Phase 1	Month 1										
	Month 2										
	Month 3										
	Month 4										
	Month 5										
	Month 6 (+/- 2 additional weeks)	X	X	X	X	X		X	X	X	X
Washout	Month 1										
	Month 2 (+/- 2 additional weeks)										
Titration	9 – 15 days		X								
Phase 2	Month 1										
	Month 2										
	Month 3										
	Month 4										
	Month 5										
	Month 6 (+/- 2 additional weeks)	X	X	X	X	X		X	X	X	X
Taper off	9 – 15 days										
FINAL VISIT	4-7 weeks later	X									

4.8 Study Schedule

\* OPTIONAL

## 5. STORAGE OF DATA AND SAMPLES

Study data will be stored in password-protected NINDS and NIH Clinical Center computer systems.

Deidentified coded CSF samples will be stored in the Laboratory of Dr [name], WSU, using the established data protection procedures of his laboratory.

## 6. ADDITIONAL CONSIDERATIONS

Research with investigational drugs or devices:

SGS-742 requires an IND.

SGS-742 will be obtained from IRIX pharmaceuticals, and encapsulated and stored by the NIH Pharmacy.

Investigator's brochure Attached

## 7. RISKS AND DISCOMFORTS

### 7.1 SGS-742

Patients are at risk for developing an allergic reaction to the study pills.

Animal toxicology studies showed development of ataxia at doses of 100-300 mg/kg in mice and rats, and seizures at > 300 mg/kg. In 6/12-month oral toxicity studies, the clear "no observable effect" level in dogs was 100 mg/kg; in rats, the only observation was a slight reduction in body weight gain in males at 200 and 600 mg/kg. Gastrointestinal and hepatic toxicity was found after administration of 300 mg/kg for three months in rats.

In the phase 2 blinded placebo-controlled study, the following side effects occurred in more than 5% of subjects:

	Active drug (n=75)	Placebo (n=35)
Diarrhea	8%	8%
Nausea	8%	6%
Dizziness	7%	3%

Side effects reported less frequently included headache, arthralgia, peripheral edema, unspecified infections, infestations, respiratory, and skin disorders. These did not differ between subjects taking active drug and placebo.

Three serious adverse events were reported. One syncopal episode occurred in a patient with a previous history of transient ischemic attacks lasted 30 minutes, resolving spontaneously without medical intervention or sequelae. One

intraocular hemorrhage occurred in a patient on warfarin. One subject had a preexisting liver function test elevation that did not change on SGS-742.

There were no clinically significant changes in laboratory tests, vital signs, weight, or ECG results.

SGS-742 is not metabolized, and >99% of the drug is excreted unchanged in urine. Thus, no clinically important drug interactions are anticipated.

Pregnancy testing and contraception:

Since the teratogenic potential of SGS-742 is unknown, women of child-bearing potential must use an effective form of birth control during the study and for a month after final drug taper is complete. Patients should not breast-feed during the study or for one month after the study is completed.

Effective methods of contraception for this study include

1. hormonal contraception (birth control pills, injected hormones or vaginal ring);
2. intrauterine device;
3. barrier methods (condom or diaphragm) combined with spermicide;
4. surgical sterilization (hysterectomy, tubal ligation, or vasectomy in a partner).

Should a subject have a positive pregnancy test, the principal investigator or lead associate investigator will meet with the family to discuss the results and will be referred to the NIH OB-gyn service for counseling. The study drug will be stopped and patients followed until pregnancy outcome.

## **7.2 MRI and MRS (OPTIONAL)**

People are at risk for injury from the MRI magnet if they have pacemakers or other implanted electrical devices, brain stimulators, some types of dental implants, aneurysm clips (metal clips on the wall of a large artery), metallic prostheses (including metal pins and rods, heart valves, and cochlear implants), permanent eyeliner, implanted delivery pump, or shrapnel fragments. Welders and metal workers are also at risk for injury because of possible small metal fragments in the eye of which they may be unaware. Subjects will be screened for these conditions before having any scan, and if they have any, they will not receive an MRI scan.

People with fear of confined spaces may become anxious during an MRI. Those with back problems may have back pain or discomfort from lying in the scanner. The noise from the scanner is loud enough to damage hearing, especially in

people who already have hearing loss. Everyone having a research MRI scan will be fitted with hearing protection. Subjects will be asked to complete an MRI screening form for each MRI scan you have. There are no known long-term risks of MRI scans.

A pregnancy test will be performed before MRI/MRS for any subject of child bearing potential. The scan will not be done if the pregnancy test is positive.

### **7.3 TMS**

Both single and paired-pulse TMS will be performed. Single pulse TMS is a minimal risk procedure. Side effects include headaches and scalp tingling. The noise of the TMS magnet can potentially damage hearing; patients will be fitted with earplugs by technicians trained to do so. Additionally, hearing in participants will be tested before and after exposure to TMS in order to check whether the TMS caused a change in hearing. If there is an auditory threshold shift of 15dB at any frequency, auditory testing will be repeated after 24 hours. If three people have a change in auditory threshold after TMS, the TMS portion of the study will no longer be carried out. Children may be more susceptible to hearing adverse events from TMS due to immaturity of the young brain and ear canal. TMS can interfere with implanted medical devices and will not be done in people who have pacemakers, implanted pumps, or stimulators, such as cochlear implants or in people who have metal objects inside the eye or skull.

Garvey et al employed a self-report questionnaire to collect children's subjective response to single-pulse TMS. They found that TMS was well tolerated by the majority of subjects, and was favorably compared to seven common childhood experiences. Notably, of the 40 children in the study, 34 subjects (85%) said they would voluntarily undergo TMS again. Because it presents no greater risk of discomfort than other potentially distressing childhood experiences of daily life, the study concluded that TMS falls within the category of no greater than minimal risk. (Garvey et al, 2001). Paired-pulse TMS carries no more than a minor increment over minimal risk.

### **7.4 Lumbar Puncture (OPTIONAL)**

Lumbar puncture is a routine clinical procedure that has a minimal level of risk of local infection and discomfort. All efforts will be made to minimize these risks, including performance of the procedure during the provision of generalized anesthesia when applicable, use of local anesthesia when generalized anesthesia is not applicable, and use of sterile technique. Post-lumbar puncture headache may occur in one-third of people, which is usually not severe and improves without treatment other than a mild pain reliever. Headaches lasting longer than 7 days develop with one in 50 to 200 lumbar punctures and usually

improve gradually over 2 weeks. In rare cases, headaches have persisted longer. Prolonged headaches may be due to persistent leakage of CSF from the area of the lumbar puncture, and will be treated with an epidural blood patch.

### **7.5 Neuropsychological testing**

Neuropsychological testing has only minor risk, including boredom and frustration.

### **7.6 Sedation**

Sedating medicines may cause decreased blood pressure, irregular heartbeats, depressed breathing, and muscle spasms. Uncommon side effects are very low blood pressure, nausea and vomiting, respiratory insufficiency, and a severe allergic reaction. On extremely rare occasions breathing may stop.

Dexmedetomidine has been shown to be a safe and well-tolerated agent, and was used without incident in our previous SSADH deficiency study. The drug is routinely used clinically in intensive care units and operating rooms, and as a sedative for individuals undergoing imaging studies (Mason 2008, Yuen 2008). According to the package insert, adverse effects in clinical trials included hypotension (28% versus 13% in patients receiving placebo, hypertension (16% versus 18%), nausea (11% versus 9%) and bradycardia (7% versus 3%).

### **7.7 EEG**

There is no risk associated with having an EEG. The patient may feel uncomfortable while the electrodes are attached to their scalp. The conductive gel sometimes causes some mild irritation. They may not like the smell of the paste or the glue remover, but they are not harmful.

### **7.8 Blood Draw**

There may be some discomfort and bruising at the site of needle entry. There is a very small risk of fainting. Infection in the area of the needle insertion is rare. 10 CC will be drawn three times during the protocol for CBC, liver function tests and electrolytes.

## **8. SUBJECT SAFETY MONITORING**

Patients will be monitored by CES Staff, including PI, nurse practitioner and fellows, and by [name], a board-certified pediatric neurologist, who is a

special volunteer with clinical privileges at NIH, and has the world's largest experience with SSADH deficiency.

[name] will serve as Independent Study Safety Monitor (ISSM). [name] is a Board-Certified Neurologist with Fellowship training in Movement Disorders who is conducting clinical research with [name].

The ISSM will serve as the IND sponsor's medical monitor and will make the final determinations of relatedness of safety events to the investigational product on behalf of the sponsor (NINDS). The ISSM will review serious adverse events, and serious unanticipated problems. SAEs that are at least temporally associated with the use of the study drug (whether assumed to be related or not) will be given to the ISSM immediately, but no later than 48hrs from the time the PI learns of an event. The PI will record nonserious AEs and report them to the ISSM at the time of 1) IRB continuing review and 2) the annual Safety Monitoring Committee's annual meeting. The ISSM will review these reports and provide feedback to the PI and NINDS in a timely manner.

Patients will be monitored carefully by CES clinicians for any change in their clinical status during clinic visits and self-report during phone and computer contact. Intervention will be determined by the independent subject safety monitor and may include consultation, additional studies, or withdrawing the patient from the protocol.

Parameters to be monitored include seizure frequency, neurological examination, fluctuations in cognitive and behavioral features. Specific drug-related side effects to be monitored include headache, tiredness, nausea and vomiting, sleepiness and dizziness.

Patients who cannot tolerate the study drug will be taken off of it. Following review and approval by the Independent Subject Safety Monitor, patients who stopped taking the study drug can remain in the study and complete follow-up visits and assessments.

Females who become pregnant will stop the study drug however will remain in the study and can be followed under the protocol. They will not complete any assessments that pose risk to the pregnancy or fetus but can do other non-invasive procedures such as neuropsychological testing. They will be followed until the end of the study or pregnancy outcome, whichever is later.

Patients will be removed from the study if they are unable to cooperate, or have an alteration in clinical status needing medical intervention. Patients may withdraw from the trial at any time at their own request. The Investigators may withdraw a subject for safety or behavioral reasons.

Toxicity will be graded according to the NCI Common Terminology Criteria for Adverse Events (appendix 2). Dose limiting toxicities will be considered any NCI grade 3 toxicity felt to be probably or definitely related to study medication; grade 4 or 5 toxicity judged to be possibly, probably or definitely related to study medication by the safety monitor.

In the event of a Grade 3 toxicity felt to be probably or definitely related to study medication by the study investigator or safety monitor, one-step dose reductions will be initiated until the toxicity resolves. If NCI Common Terminology Grade 4 toxicity is felt to be possibly, probably or definitely related to study medication by the study investigator, the patient will be withdrawn from the study medication. All dose changes and/or dose interruptions will be recorded on case report forms.

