### **8.1 Criteria for Breaking the Blind and Premature Termination or withdrawal**

Criteria to be used to decide whether a report or test result requires intervention include Grade 3 NCI CTC toxicity, a laboratory test twice the upper limit of normal, an abnormal finding on EEG or ECG not present at baseline. Intervention will be determined by the safety monitor and may include consultation, additional studies, or withdrawing the patient from the protocol.

The blind for an individual may need to be broken even for non-serious, expected, or unrelated AEs or as requested by local regulatory authorities or where, in the view of the safety monitor, knowledge of the identity of the study drug is essential to appropriately manage an adverse event.

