Seizures are a clinical feature of SSADH and an expected event for this population. This patient population may experience seizures and resulting emergency room visits and/or hospitalization. We will record these events including the resulting emergency room visits and/or hospitalization as part of the adverse events reported at the time of continuing review. Reporting of seizures

and emergency-related treatment at the time of the CR is limited to emergency related seizure treatment only and all other SAEs will be reported immediately.

The ISSM will serve as the IND sponsor's medical monitor and will make final determination of relatedness of safety events to the investigational product on behalf of the sponsor (NINDS). The PI will immediately (no later than 48hrs) report SAEs that are at least temporally associated with the use of the study drug to the ISSM according to the requirements of 21 CFR 312.64(b) and as agreed upon with the sponsor. The PI will record nonserious AEs and report them to the ISSM at the time of 1) IRB continuing review and 2) the annual Safety Monitoring Committee's annual meeting. The PI will send the AE log to the IRB with the next continuing review.

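### Section 8 orders removal from the study for any clinical change needing medical intervention, in conflict with the monitor-discretion, dose-reduction and stay-in-study rules in Sections 8 and 8.1

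*Combined protocol and SAP*

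**What the plan says.** All references are to the combined protocol and SAP.

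- **Section 8, removal sentence:** "Patients will be removed from the study if they are unable to cooperate, or have an alteration in clinical status needing medical intervention". Shortly afterwards the same paragraph gives investigators the option, not the duty, to withdraw a subject on safety or behavioural grounds.
- **Section 8, response to a clinical change:** the independent safety monitor decides on the intervention, which "may include consultation, additional studies, or withdrawing the patient from the protocol".
- **Section 8, patients off drug:** once the monitor has reviewed and approved, "patients who stopped taking the study drug can remain in the study and complete follow-up visits and assessments".
- **Section 8, toxicity:** for Grade 3 judged probably or definitely related, "one-step dose reductions will be initiated until the toxicity resolves". For Grade 4 judged at least possibly related, "the patient will be withdrawn from the study medication".
- **Section 8.1:** "Criteria to be used to decide whether a report or test result requires intervention include Grade 3 NCI CTC toxicity", along with certain laboratory, EEG and ECG findings. It then says: "Intervention will be determined by the safety monitor and may include consultation, additional studies, or withdrawing the patient from the protocol".
- **Section 17:** seizures are an expected event. "This patient population may experience seizures and resulting emergency room visits and/or hospitalization"; these are recorded and reported at continuing review.
- **Sections 4.1.1 and 4.4:** a seizure shifts the schedule, and TMS and MRS are rebooked if one was reported in the preceding 24 hours.

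**The concern.** The removal sentence and its neighbours address overlapping events but give different outcomes. One is automatic and acts on the study; the others are graded or discretionary, and several act only on the drug. Staff following the protocol could reach opposite dispositions for the same patient.

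This matters for the analysis because Section 10.1 plans a paired comparison of placebo and SGS-742. A patient taken out of the study before an end-of-phase assessment contributes no complete pair, even where another sentence of Section 8 would have allowed the score to be collected. If the events that trigger removal are affected by the drug, the patients who complete are selected on something that treatment may influence.

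**Working it through.** **Step 1. Set the rules side by side.**

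| Situation | Removal sentence, Section 8 | Other text | Can both be applied? |
|---|---|---|---|
| Change in clinical status that needs intervention | Out of the study, no discretion | Sections 8 and 8.1: monitor decides; withdrawal is one of three options | No |
| Safety reason for withdrawal | Out of the study | Section 8: investigators may withdraw | No; mandatory against optional |
| Related Grade 3 toxicity that needs medical treatment | Out of the study | Section 8: stepwise dose reduction until resolution | No; a patient already removed cannot be stepped down |
| Drug stopped because of an event that needed treatment | Out of the study | Section 8: may stay and be assessed, after monitor approval | No |
| Seizure treated in an emergency room or hospital | Could be out of the study | Section 17: expected, recorded; Sections 4.1.1 and 4.4: reschedule | Depends on an undefined term |

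The first four rows do not depend on how seizures are classified. The fifth does: the protocol does not define an alteration in clinical status, and no sentence exempts seizures from removal. Section 4.7 adds that study physicians may help manage neurologic treatment during participation, which fits poorly with a rule that needing treatment ends participation.

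**Step 2. Follow the data.** Testing takes place at baseline and at the end of each six-month phase (Sections 4.4 and 4.8).

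- Removal in phase 1: neither on-treatment score is obtained.
- Removal in phase 2 before its final assessment: the phase 1 score exists and the phase 2 score does not.

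Either way the within-patient difference between SGS-742 and placebo cannot be formed from observed data.

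**Step 3. Ask whether the loss could depend on treatment.** Section 8 lists seizure frequency and drug side effects as monitored parameters. Section 1.2.2 reports shorter spike-wave discharges on SGS-742 in mice. Section 7.1 reports seizures in mice and rats above 300 mg/kg, against a trial target of 10 mg/kg per dose (Section 4.5.2). Dependence on treatment is therefore possible; its direction and size are not known.

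**Step 4. Reproduce the plan's sample size, for scale.** Inputs from Section 10.1: paired t-test, 0.75 SD, 16 completers, 22 enrolled. Alpha and power are not stated; two-sided 0.05 and 80% are assumed, with 0.75 taken as a multiple of the SD of the within-patient difference. Power is the probability that a noncentral t with n − 1 degrees of freedom and noncentrality 0.75 × √n exceeds the two-sided critical value.

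- n = 16: noncentrality 0.75 × 4 = 3.0, power 80.1%. This is the smallest n reaching 80%, so the plan's figure reproduces.
- n = 15: power 77.1%.
- n = 22: power 91.8%.
- Dropout allowance: 22 − 16 = 6 patients; 6/22 = 27.3%.

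At the target of 16, one unreplaced lost pair costs about 3 percentage points of power (80.1 − 77.1). Replacement can restore the count. It does not restore the removed patient's comparison.

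**The case against.** Several points on the other side are sound and limit the conclusion.

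**Seizures.** A reader might infer that the sentence would remove every patient with a treated seizure. The documents do not support that. In a disease where seizures are expected, a habitual seizure need not count as an alteration, and the rescheduling text suggests that such patients are meant to stay. What stands is that the sentence could be applied that way.

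**Count.** It is tempting to multiply the 45% seizure figure in Section 1 by 22 (9.9 patients) and assume a share removed. The 45% comes from a questionnaire and interview study of clinical history, is not an on-study rate, and precedes this trial's exclusion of patients who need vigabatrin or benzodiazepines (Section 3.3). No share is given. Letting it run from 0 to 100% gives 0 to 9.9 removals, a range that includes the allowance of six and so settles nothing.

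**Grade 3.** A toxicity handled by dose reduction alone might not be regarded as needing medical intervention. The conflict is then confined to toxicity that also needs treatment. That case remains.

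**Retention.** The Grade 4 rule stops the drug but does not say that the patient stays, and remaining off drug requires the monitor's prior approval. Neither guarantees retention. The conflict is between automatic removal and an approval route that automatic removal would close.

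**Mitigation.** Section 10.1 records reasons for dropout and allows for sensitivity analyses, including a worst-case assumption and imputation. Section 3.1 replaces those who leave before three months of the second phase, and Section 10.1 replaces dropouts until there are 16 completers. These protect the number and probe the result, but they put assumptions in place of scores that the approval route could have kept.

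**Tolerability.** A reader might also infer that tolerability problems would be under-reported. That does not follow: adverse events are recorded and summarised (Section 17), as are reasons for dropout (Section 10.1).

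**Conclusion.** The concern holds as an internal contradiction with a consequence for the primary comparison. The removal sentence in Section 8 cannot be applied together with the monitor-discretion text in Sections 8 and 8.1, the optional-withdrawal sentence, the Grade 3 dose-reduction rule where treatment is also needed, or the approval route for patients off drug. Its reach to treated seizures is possible and rests on an undefined term.

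Each removal before the remaining end-of-phase assessment loses one SGS-742/placebo pair out of a target of 16, and the loss may be related to treatment. Neither the number of removals nor the direction of any bias can be estimated from the documents. The textual conflict needs no numerical assumption; only the power figures rest on the assumed alpha and SD definition.

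**What to change.** The sponsor should reconcile Sections 8, 8.1 and 17 so that a single rule governs each event, and should decide which clinical rule that is. For the analysis, the amended text should:

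1. Separate stopping or changing study drug from leaving the study, and say which of the two each trigger leads to.
2. Say what counts as an alteration in clinical status, including whether an expected seizure that receives medical care falls under it.
3. State that patients who stop drug but remain under the existing route, with the safety monitor's prior review and approval, still have the scheduled end-of-phase assessments collected. The approval requirement stays as written.

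The cost is a short protocol amendment. The downside is that a few off-drug patients attend visits that are already scheduled.
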